6.2.2 Enrollment, Baseline, and/or Randomization

Enrollment

Enrollment is defined as the date of randomization at which point all eligibility criteria are confirmed and the individual has agreed to participate; this is recorded on a case-report form. AEs will be collected after the participant is enrolled. Participants will be told to contact study staff and/or providers about any health-related changes they experience. 40-50 participants will be enrolled.

Baseline Assessments

Baseline measures will include demographic, occupational, clinical and behavioral characteristics, and mediating outcomes including the NIH Research Task Force's minimum dataset for chronic LBP.¹¹¹ The following will be collected at baseline:

- Demographics including PhenX ToolKit's core measures for Social Determinants of Health¹⁵⁵
- Quebec Task Force Classification for spinal disorders⁹⁵ and Pain Detect Questionnaire to identify neuropathic presentations of BRLP¹⁵⁶
- STarT Back Screening tool¹¹²

Clinical Outcome Measures

- BRLP and LBP frequency over the past week (number of days with BRLP symptoms).
- BRLP and LBP intensity (0-10 pain scale) over the past week using the ordinal 11-box NRS (0=no BRLP/LBP, 10=the worst BRLP/LBP possible).
- Disability will be measured with the 23-item Roland Morris Disability Questionnaire which was adapted and validated for BRLP.¹¹⁵
- PROMIS-29 +2 includes measures of pain interference with normal activities, physical function, fatigue, sleep disturbance, anxiety, depression, and participation in social roles and activities.¹¹⁶⁻¹¹⁸ The PROMIS-29+2 also provides a preference-based summary of health-related quality of life.¹¹⁹ Other PROMIS/NIH Toolbox instruments will include social emotional support;^{116,117} domain-specific life satisfaction (e.g. work, family, housing);¹²⁰ and perceived stress.¹²²
- Productivity loss related to BRLP (e.g., missed work, reduced productivity while at work) will be assessed using questions from the Institute for Medical Technology Assessment's productivity cost questionnaire.¹²³

Behavioral Outcomes

The following behavioral outcomes are chosen because they're most likely to affect the experimental intervention:

- Chronic pain coping behaviors will be measured using the Chronic Pain Coping Inventory - 2-item version.¹²⁸
- Over-the-counter and prescription medication use²⁰ for BRLP, including class of medication and frequency of use.

- Healthcare use for BRLP including MRIs, injections, hospitalizations, surgeries, and provider-based visits.²⁰
- Physical activity levels (e.g. amount of sedentary activity) measured with the International Physical Activity Questionnaire.¹²⁹

Mediating Outcomes

Mediating outcomes and targets of the intervention theorized to affect the clinical and behavioral outcomes will also be collected to inform protocol refinement. These include:

- BRLP related capabilities (e.g. knowledge, skills, physical capacity), opportunities (e.g. available resources), motivations (e.g. optimism)⁵¹⁻⁵³ for participants enrolled into supported self-management.
- Beliefs related to self-efficacy as measured by confidence in ability to manage daily activities, symptoms, emotions, and social interactions (PROMIS self-efficacy for managing chronic conditions);¹³⁰ the chronic pain acceptance questionnaire will also be administered.¹⁵⁷
- Fear-avoidance beliefs using the Fear-avoidance Beliefs Questionnaire¹³¹
- Catastrophizing measured using the 13-item Pain Catastrophizing Scale;¹³² it uses a 5-item point scale (0=not at all, 4 all the time) and has internal consistency and validity.
- Expectations about back pain treatments (HEAL items).¹³⁵

Qualitative measures

Qualitative measures will be collected from enrolled subjects, as well as providers regarding their views of barriers, facilitators, affordability, practicality, effectiveness, acceptability, and equity.

As part of the supplemental aims, qualitative information will be collected from other stakeholders with pain who are underrepresented in CIH LBP/BRLP research to explore their views of barriers and facilitators to care for LBP/BRLP.

Randomization

In the pilot study, randomization precedes intervention administration. Randomization will occur within 21 days of completing the first baseline screening visit. Participants who are not randomized within this time frame will repeat the in-person screening. Interventions will be initiated within 14 days of randomization/enrollment.

6.2.3. Blinding

Blinding of treatment providers and participants is not feasible. However, the following steps will be taken to minimize potential bias and enhance study rigor:

- Study personnel involved in screening and enrollment will be masked to upcoming randomization assignments
- The statistician will be blinded to treatment group until the analysis is complete.

- Participants will be queried in self-report questionnaires as to whether or not anybody attempted to influence their responses.

Blinded Personnel: Select investigators and the study statistician will be blinded until the database is locked and the analysis is complete. The study's statistician will assign a member of his staff to create the random allocation tables according to the allocation plan, which will be administered using the randomization module in REDCap.

Unblinded Personnel: The study coordinator, clinicians, data manager, and investigators participating in fidelity assessment will not be blinded to study interventions.

Individuals authorized to break the blind: The PIs and their investigator designees are authorized to break the blind.

Circumstances for breaking the blind: This will occur when it is in the participants' safety-related interest. The primary example is a reportable adverse event.

6.2.4 Follow-up Visits

Intervention Visits (M0-M6)

The following information will be collected at each intervention visit in the pilot study, which will occur as needed throughout the six months, as there is no set schedule of treatments:

- Treatment administered – study providers will record treatment administered at each visit including required, allowed, and prohibited treatments.
- Adverse events (AEs)- participants will be asked about the occurrence of AE/SAEs by their treatment provider at each visit. The AE protocol described in section 7, Safety and Assessments will be initiated and adhered to for all AEs identified.

Weekly Follow-Up (\pm 3 DAYS)

Weekly outcomes will be collected electronically via direct patient self-report for six months; participants who are unable to provide electronic data will be contacted directly by blinded study staff who will ascertain outcomes. Additional information related to data collection and quality assurance is described in section 10.

Clinical Outcome Measures

- BRLP and LBP frequency and intensity

Monthly Follow-up (\pm 14 DAYS)

Monthly follow-up data (Months 1-6) will be collected electronically via direct patient self-report. Participants who are unable to provide electronic data will be contacted directly by blinded study staff who will ascertain outcomes, or they will be mailed a paper copy of the questionnaire to complete and return to the study team. Additional information related to data collection and quality assurance is described in section 10.

The following outcomes will be collected on a monthly basis for 6 months (\pm 14 days):

Clinical Outcome Measures

- Disability, PROMIS-29+2 measures, and productivity loss
- Adverse Events - participants will be asked if they experienced any potential adverse events associated with study interventions (e.g. increased pain, neurological symptoms, nausea)

Behavioral Outcome Measures

- BRLP-related medication and healthcare use

Month 2 Follow-up (\mp 14 DAYS)

Mediating Outcome Measures

- Satisfaction related to the patient-provider connection and healthcare environment (HEAL items).¹³⁵ Treatment expectations for the assigned intervention will also be assessed.

Month 3 Follow-up (\mp 14 DAYS)

Clinical Outcome Measures

- PROMIS/NIH Toolbox measures for social emotional support, domain-specific life satisfaction, and perceived stress.
- Global improvement will be measured using a 9-point scale ranging from completely recovered to vastly worse.¹⁵⁴

Behavioral Outcome Measures

- Chronic pain coping behaviors, physical activity levels

Mediating Outcome Measures

- BRLP related capabilities (e.g. knowledge, skills, physical capacity), opportunities (e.g. available resources), motivations (e.g. optimism) for participants enrolled in SSM⁵¹⁻⁵³
- Beliefs regarding self-efficacy, fear avoidance, and treatment.
- Satisfaction related to the patient-provider connection, healthcare environment (HEAL items),¹³⁵ specific components of the SBSM intervention, and overall treatment²⁰

Qualitative Measures

For the pilot study, qualitative data will be collected via open-ended questions in REDCap surveys, as well as semi-structured, audio-recorded interviews.¹⁰⁶ Patient and provider views of barriers, facilitators, affordability, practicality, effectiveness, acceptability, equity will be collected.

Month 6 Follow-Up & Final Close Out/Final Evaluation (-14 to +28 DAYS)

Clinical Outcome Measures

- PROMIS/NIH Toolbox measures for social emotional support, domain-specific life satisfaction, and perceived stress
- Global improvement

Behavioral Outcome Measures

- Chronic pain coping behaviors, physical activity levels

Mediating Outcome Measures

- Beliefs regarding self-efficacy and fear avoidance.
- Satisfaction related to the patient-provider connection, healthcare environment (HEAL items),¹³⁵ specific components of study interventions, and overall treatment²⁰

Participant Close-out

- Final participation will be used to record participant status. Participants will receive notice of their participation being complete (via email or mail).

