7. SAFETY ASSESSMENTS

7.1. AEs and SAEs, Expectedness, and Relatedness- Definitions

The Co-PIs are responsible for adjudicating AEs/SAEs.

Adverse Event

AE is generally defined as any unfavorable and unintended diagnosis, symptom, sign (including an abnormal laboratory finding), syndrome or disease which either occurs during the study, having been absent at baseline, or if present at baseline, appears to worsen. AEs are to be recorded regardless of their relationship to the study intervention.

The following scale will be used to grade AEs:

1. Mild: no intervention required; no impact on activities of daily living (ADL).
2. Moderate: minimal, local, or non-invasive intervention indicated; moderate impact on ADL.
3. Severe: significant symptoms requiring invasive intervention; subject seeks medical attention, needs major assistance with ADL.

We will measure and compare rates of AEs across the two treatment arms. We will specifically look for common treatment-related AEs that include: LBP, soreness at the treatment site, gastrointestinal symptoms, emotional discomfort, and other events. We will capture AEs prospectively from study participants through monthly surveys and at intervention visits. Each unique occurrence will receive a separate ID in order to avoid duplication in documentation.

Serious Adverse Event

SAE is generally defined as any untoward medical occurrence that

- results in death
- is life threatening
- requires inpatient hospitalization or prolongation of existing hospitalization

- results in persistent or significant disability/incapacity, or is
- a congenital anomaly or birth defect.

We will collect SAEs both passively through ad hoc reporting and through systematic evaluation at study visits. Given the nature of the interventions we do not anticipate any specific treatment-related SAEs and therefore focus on standard and BRLP-specific serious events: death; severe or permanent disabilities; life-threatening conditions; hospitalizations; other important medical events; progressive neurological deficits, or cauda equina syndrome.

Expectedness:

AEs and SAEs will be classified as expected if

- They have been documented as a known adverse reaction (disclosed in the consent form) or are part of an existing comorbid disease process. The PI or designee is responsible for making this determination.

Relatedness to Research Participation:

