AEs and SAEs will be classified as either unrelated, unlikely related, possibly related, probably related, or definitely related to participation in the research project. The PI or designee is responsible for making this determination. To assess relationship of an event to study intervention, the following guidelines are used:

Related (Possible, Probable, Definite)

- The event is known to occur with the study intervention.
- There is a temporal relationship between the intervention and event onset.
- The event abates when the intervention is discontinued.
- The event reappears upon a re-challenge with the intervention.

Not Related (Unlikely, Unrelated)

- There is no temporal relationship between the intervention and event onset.
- An alternate etiology has been established.

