7.2 Adverse Event Identification

Adverse events will be identified in the following ways:

- Following enrollment, participants will be asked about the occurrence of AE/SAEs by their treatment provider at every visit.
- Participants will be informed to report AE/SAEs directly to study staff throughout the study period
- Participants will be asked if they experienced any AE/SAEs during their monthly self-report questionnaires.

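### Section 6.2.4 limits the monthly adverse-event question to events tied to the study treatments, although 7.1 and 7.2 call for all adverse events

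*Combined protocol and SAP*

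**What the plan says.** Section 6.2.4, under Monthly Follow-up, describes the item as follows: "participants will be asked if they experienced any potential adverse events associated with study interventions (e.g. increased pain, neurological symptoms, nausea".

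Section 7.2 describes the same survey without that limit: "Participants will be asked if they experienced any AE/SAEs during their monthly self-report questionnaires".

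Section 7.1 sets the recording rule: "AEs are to be recorded regardless of their relationship to the study intervention". It names the monthly surveys and the intervention visits as the two prospective sources of AE data. Judging relatedness is a later and separate step, graded from unrelated up to "definitely related to participation in the research project. The PI or designee is responsible for making this determination". Section 7.1 also commits to a comparison: "We will measure and compare rates of AEs across the two treatment arms".

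Three other features bear on the point. Intervention visits happen as needed, "as there is no set schedule of treatments". The monthly healthcare item covers only "BRLP-related medication and healthcare use". Section 6.2.3 states that participants cannot be blinded.

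**The concern.** One questionnaire is described in two ways, and the narrower description is the one that sits with the survey content. Someone building the form from Section 6.2.4 could reasonably produce an item that asks only about effects of treatment. The participant would then be filtering for relatedness before the PI or designee sees anything, although Section 7.1 gives that judgement to the PI or designee and asks for all events.

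Two things are at stake. The first is completeness. Inpatient hospitalization is an SAE under Section 7.1 whatever its cause, and Table 8 in Section 10.3.6 sends even expected or unrelated SAEs to the PI and Steering Committee per occurrence. An admission that is never reported cannot be adjudicated or passed on. The second is comparability. The monthly item is the only active AE question put to both arms on the same timetable. Participants know their arm, so an item that depends on what they attribute to treatment could be answered differently in the two arms.

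**Working it through.** No arithmetic applies; the check is a comparison of text.

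**Step 1. The descriptions side by side.**

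| Place | Scope of AE collection | Relatedness limit? |
|---|---|---|
| 6.2.4, Monthly Follow-up | Potential events tied to the study treatments, with three examples | Yes |
| 7.2 | Any AE or SAE in the monthly questionnaire | No |
| 7.1 | All AEs; monthly surveys named as a source | No |
| Table 5 (6.1) | Adverse events at monthly follow-up | No |

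The first row disagrees with the other three. All four are current text, and no section gives one precedence over another.

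**Step 2. Two readings of the 6.2.4 item.** It may ask participants whether an event came from their treatment, or it may be a checklist of known treatment effects that asks for no causal judgement. The first can lose events that participants consider unrelated. The second can lose events that are not on the list. Both are narrower than 7.2. Under either reading, increased pain, neurological symptoms and nausea are likely to be caught, because they are the stated examples.

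**Step 3. Follow one event through each route.** Take an admission for a condition other than back-related leg pain, with the survey built as in 6.2.4:

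- *Monthly AE item:* can be answered no.
- *Monthly healthcare-use item:* limited to back-related leg pain (6.2.2 and 6.2.4), so it does not ask about this admission.
- *Weekly survey:* covers only pain frequency and intensity (6.2.4).
- *Provider question:* asked at every visit without a relatedness limit (7.2), but only if there is a visit. After week 12, further study care is optional and is offered when leg pain returns or gets worse (Section 5).
- *Spontaneous report:* open throughout (Table 5 footnote, 6.2.2, 7.2), but it relies on the participant coming forward.
- *PI and Steering Committee review (10.3.4):* sees only what has already been reported.

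The event can therefore still be caught, but for a participant with no visits after week 12 the only scheduled AE question in that period is the monthly item.

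**Step 4. Timetable by arm.** Section 5.4 expects 6-10 visits for most SSM participants and 2-4 for most medical-care participants. Provider questioning therefore does not run on a common schedule. The monthly item does, at months 1 to 6 in both arms.

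**Step 5. What cannot be computed.** The documents give no admission rate and no under-reporting rate, so neither a probability nor a number of missed events can be derived.

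**The case against.** The strongest reply is that Section 7 governs. Section 7.2 is the section devoted to AE identification, and it is already correct. Table 5 carries no qualifier, and the intervention-visit bullet in 6.2.4 itself defers to Section 7. The monthly bullet may be a staff-facing summary of the targeted look for common treatment effects that 7.1 also mentions. In addition, 6.2.2 tells participants to contact the study about any change in their health, which needs no attribution.

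Much of this stands. It makes loss of an event possible and not certain, and it means the survey may already be worded correctly. It does not settle the matter: the deferral is not in the monthly bullet, no precedence is stated, and the targeted look in 7.1 sits inside the all-AE rule.

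Several stronger readings might be inferred, and the documents do not support them:

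- *That SAEs are not sought in the monthly survey*, because 7.1 says "We will collect SAEs both passively through ad hoc reporting and through systematic evaluation at study visits". Section 6.2.4 places monthly follow-up under a heading of follow-up visits, 7.2 names SAEs in the monthly questionnaire, and 7.3 gives a procedure for SAEs found at monthly follow-up. The gap is largely closed.
- *That serious NSAID complications would go unseen.* Cardiovascular events and gastrointestinal bleeding are listed risks (7.5), and providers discuss drug-specific risks before prescribing (5.1.2). Participants are relatively likely to link such events to the drug.
- *That the danger is greatest after week 12.* The documents show fewer assured contacts then, but not a higher risk of events or of missed events.
- *That the arm comparison is biased in a known direction.* Nothing shows which arm would under-report.

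**Conclusion.** The point holds as an inconsistency in safety data collection: the monthly item in 6.2.4 is narrower than 7.1 and 7.2 require. Confidence in the mismatch is high. The consequence is conditional on the unseen questionnaire following 6.2.4. In that case, events that are unlisted or that participants consider unrelated can be missed, and the existing safeguards reduce that risk without removing it.

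The size is modest and cannot be put as a rate. This is a feasibility pilot of 40-50 participants. AEs are neither primary nor secondary outcomes (9.4.1, 9.4.2), and 9.5 sets out no AE analysis. The correction is still worth making, because 7.1 promises a between-arm comparison of AE rates and the pilot's methods are meant to feed the later multi-site trial (Section 14).

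**What to change.** Reword the monthly item in 6.2.4 to match 7.2, for example: *Since your last survey, have you had any new or worse health problem (such as increased pain, neurological symptoms or nausea), or been admitted to hospital for any reason, whether or not you think it is linked to the study?* The current examples stay as prompts, and relatedness stays with the PI or designee.

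Naming the monthly surveys in the SAE collection sentence of 7.1 is optional tidying.

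The cost is small: one survey item and one bullet of protocol text, with no new visits or forms. Section 11.1 requires IRB approval of changes to the protocol and to participant-facing forms. If the survey already follows 7.2, only the protocol text needs changing. Staff should expect a few more unrelated events to follow up and log, which 7.1 already requires.

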6.2.5. Compensation

There is no cost for participation in the study. Participants and their insurers will not be billed for study screening and treatment visits. Participants in the pilot study will be compensated a total of \$150.00 for time associated with participating in the study, in the form of a UMN ClinCard. Participants are not compensated for attending screening and/or intervention study visits. ClinCards will be administered at an in-person study visit or via mail following enrollment in the study. The following compensation scheduled will be used:

80% of weekly surveys completed	\$40.00
Month 1 follow-up completion	\$10.00
Month 2 follow-up completion	\$10.00
Month 3 follow-up completion	\$40.00
Month 4 follow-up completion	\$10.00

Month 5 follow-up completion	\$10.00
Month 6 follow-up completion	\$30.00

In addition, prescription and over-the-counter medications recommended for participants in the MC group will be paid for by the study. Study staff will load cards with funds for participants to pay for their study medications. ClinCards will be administered at an in-person study visit or via mail following enrollment in the study.

For the supplemental aims qualitative interviews, participants will be compensated \$50.00 per interview.

7. SAFETY ASSESSMENTS

7.1. AEs and SAEs, Expectedness, and Relatedness- Definitions

The Co-PIs are responsible for adjudicating AEs/SAEs.

Adverse Event

AE is generally defined as any unfavorable and unintended diagnosis, symptom, sign (including an abnormal laboratory finding), syndrome or disease which either occurs during the study, having been absent at baseline, or if present at baseline, appears to worsen. AEs are to be recorded regardless of their relationship to the study intervention.

The following scale will be used to grade AEs:

1. Mild: no intervention required; no impact on activities of daily living (ADL).
2. Moderate: minimal, local, or non-invasive intervention indicated; moderate impact on ADL.
3. Severe: significant symptoms requiring invasive intervention; subject seeks medical attention, needs major assistance with ADL.

We will measure and compare rates of AEs across the two treatment arms. We will specifically look for common treatment-related AEs that include: LBP, soreness at the treatment site, gastrointestinal symptoms, emotional discomfort, and other events. We will capture AEs prospectively from study participants through monthly surveys and at intervention visits. Each unique occurrence will receive a separate ID in order to avoid duplication in documentation.

Serious Adverse Event

SAE is generally defined as any untoward medical occurrence that

- results in death
- is life threatening
- requires inpatient hospitalization or prolongation of existing hospitalization

- results in persistent or significant disability/incapacity, or is
- a congenital anomaly or birth defect.

We will collect SAEs both passively through ad hoc reporting and through systematic evaluation at study visits. Given the nature of the interventions we do not anticipate any specific treatment-related SAEs and therefore focus on standard and BRLP-specific serious events: death; severe or permanent disabilities; life-threatening conditions; hospitalizations; other important medical events; progressive neurological deficits, or cauda equina syndrome.

Expectedness:

AEs and SAEs will be classified as expected if

- They have been documented as a known adverse reaction (disclosed in the consent form) or are part of an existing comorbid disease process. The PI or designee is responsible for making this determination.

Relatedness to Research Participation:

AEs and SAEs will be classified as either unrelated, unlikely related, possibly related, probably related, or definitely related to participation in the research project. The PI or designee is responsible for making this determination. To assess relationship of an event to study intervention, the following guidelines are used:

Related (Possible, Probable, Definite)

- The event is known to occur with the study intervention.
- There is a temporal relationship between the intervention and event onset.
- The event abates when the intervention is discontinued.
- The event reappears upon a re-challenge with the intervention.

Not Related (Unlikely, Unrelated)

- There is no temporal relationship between the intervention and event onset.
- An alternate etiology has been established.

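### Minor: the planned between-arm comparison of AE rates pools an evenly scheduled source with one that is unequal by design, and the monthly AE item is described inconsistently

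*Combined protocol and SAP*

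**What the plan says.** Section 7.1 states "We will measure and compare rates of AEs across the two treatment arms" and names two prospective sources: "We will capture AEs prospectively from study participants through monthly surveys and at intervention visits". It also sets the recording rule: "AEs are to be recorded regardless of their relationship to the study intervention". Each unique event gets its own ID so that it is not counted twice.

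Section 7.2 gives three routes into the record:
- **Provider questioning:** "participants will be asked about the occurrence of AE/SAEs by their treatment provider at every visit".
- **Direct report:** "Participants will be informed to report AE/SAEs directly to study staff throughout the study period". Section 6.2.2 and the footnote to Table 5 say much the same.
- **Monthly survey:** "Participants will be asked if they experienced any AE/SAEs during their monthly self-report questionnaires".

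Section 6.2.4 describes that monthly item differently: "participants will be asked if they experienced any potential adverse events associated with study interventions (e.g. increased pain, neurological symptoms, nausea". Section 7.1 leaves the judgement of relatedness to the PI or designee.

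Section 5.4 anticipates 6-10 visits for most SSM participants and 2-4 for most MC participants. Section 9.5 covers feasibility and protocol-refinement measures and contains no AE analysis. Table 8 sends AE rates to the PI, Steering Committee, independent monitors and NCCIH, without saying whether by arm or by source.

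**The concern.** The monthly survey and the invitation to report directly are the same in both arms. Provider questioning is not: it follows the visit schedule, which differs by design. Even the adherence minima differ (6 against 2 in Section 5.4). Table 6 gives 4 against 2; the two SSM figures need reconciling, but the minima are unequal under either. De-duplication by ID prevents double counting but cannot recover an event that nobody asked about. If the surveys miss events, the arm questioned more often will tend to have more of its events recorded.

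What is at stake is interpretation. Without the source shown, a reader cannot tell how much of a difference reflects questioning and how much reflects treatment. The pilot exists to refine methods for a larger trial of the same two approaches. A larger sample shrinks sampling error but not unequal questioning.

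The wording of the monthly item is a separate matter. Taken literally, Section 6.2.4 would have participants screen events for relatedness before reporting them, a task that Section 7.1 gives to the PI or designee.

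**Working it through.** The plan gives no AE-rate calculation to reproduce.

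**Prompts, from the documents**
- Visits only: from 6/4 = 1.5 to 10/2 = 5.0 (SSM:MC).
- With six monthly surveys added: SSM 12-16, MC 8-10; from 12/10 = 1.2 to 16/8 = 2.0.

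A ratio of prompts is not a ratio of captured events, so a capture model is needed. Everything in it beyond the visit numbers and calendar is my assumption.

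**Assumptions.** True event rates are equal in the arms and constant over 26 weeks (182 days). Visits are evenly spread over weeks 1-12 (84 days), with none later. A visit picks up events that began in the preceding w days, with w = 7 or 28. Surveys capture a share s of the remaining events. There is no direct reporting.

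**Formulas**
- Visit coverage in weeks 1-12: c = min(1, w × n/84) for n visits.
- Captured share, weeks 1-12: s + (1 − s) × c.
- Captured share, six months: s + (1 − s) × c × 84/182, where 84/182 = 0.4615.

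**Coverage.** For w = 7: n = 10 gives 0.833, n = 6 gives 0.500, n = 4 gives 0.333, n = 2 gives 0.167. For w = 28: n = 2 gives 0.667, and n of 3 or more gives 1.

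**Worked case: s = 0.5, w = 7, six months**
- 10 vs 2 visits: (0.5 + 0.5 × 0.833 × 0.4615)/(0.5 + 0.5 × 0.167 × 0.4615) = 0.692/0.538 = 1.29.
- 6 vs 4 visits: 0.615/0.577 = 1.07.

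**Captured-rate ratio SSM/MC, all anticipated visit pairings**

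| Survey capture s | Six months, w = 28 | Six months, w = 7 | Weeks 1-12, w = 28 | Weeks 1-12, w = 7 |
|---|---|---|---|---|
| 100% | 1.00 | 1.00 | 1.00 | 1.00 |
| 85% | 1.00-1.03 | 1.01-1.05 | 1.00-1.05 | 1.03-1.11 |
| 70% | 1.00-1.06 | 1.03-1.13 | 1.00-1.11 | 1.06-1.27 |
| 50% | 1.00-1.12 | 1.07-1.29 | 1.00-1.20 | 1.13-1.57 |

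**Spurious excess in participants with any AE.** Take 35% as the true proportion in each arm over the window considered. That is the earlier-trial figure in Section 5.1.1, used only for illustration. The recorded proportion is 1 − exp(−0.431 × captured share), with 0.431 = −ln(0.65). At s = 0.5 and w = 7:
- Six months, 10 vs 2: 25.8% − 20.7% = 5.1 points. For 6 vs 4: 1.3 points.
- Weeks 1-12, 10 vs 2: 32.6% − 22.2% = 10.4 points. For 6 vs 4: 2.6 points.

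**Sampling error.** The 95% half-width for an arm difference at 35% is 1.96 × √(2 × 0.35 × 0.65/n): 29.6 points for n = 20 per arm and 26.4 for n = 25.

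**Survey-only rates can err the other way.** Suppose short-lived events are 60% of SSM and 30% of MC events, and the survey captures 50% of short-lived and 70% of other events (again assumptions). The survey-only ratio is (0.6 × 0.5 + 0.4 × 0.7)/(0.3 × 0.5 + 0.7 × 0.7) = 0.58/0.64 = 0.91.

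**The case against.** **Nothing turns on it.** Sections 9.4.1 and 9.4.2 list only feasibility and refinement outcomes, and no test, margin or rule uses AE rates. In a pilot of 40-50, sampling error exceeds every excess computed above. This stands, and is why the point is minor. It does not remove the comparison that Section 7.1 promises.

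**The high ratios need unfavourable inputs.** No section states a 7-day look-back. At 28 days the ratio is exactly 1.00 whenever MC has three or more visits. Section 10.3.4 aims for 85% or higher on each follow-up survey, and Section 2.2 reports 98% for monthly surveys in the team's earlier pilot. At those completion rates, 50% capture means omitting 1 − 0.5/0.85 = 41% to 1 − 0.5/0.98 = 49% of events on completed surveys. This largely stands, although completing a survey is not the same as reporting every event on it.

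**The source is probably on file already.** Section 5 says side effects are documented visit by visit on standardized forms. Section 10.1 has a form for every visit, while surveys are separate electronic instruments. This stands, although linkage to the AE ID is not described.

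**Stronger readings that the documents do not support.** A reader might infer that the comparison will overstate harm in SSM. Direction is not established: the earlier trial in Section 2.2 saw fewer expected AEs in the arm that added manipulation sessions, a contrast that also reflects treatment effects, and more SSM visits also mean more treatment exposure. A reader might also infer that the survey leaves out unrelated events. The item itself is not in the documents, and Section 6.2.4 may be loose paraphrase. Participants are also told: "Participants will be told to contact study staff and/or providers about any health-related changes they experience".

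**Conclusion.** The point holds as a minor one. Section 7.1 compares AE rates that pool a source scheduled equally with one that is unequal by design, and no section separates them, so an all-source difference may partly reflect how often participants were asked. The documents fix neither the size nor the direction. On the stated assumptions, the six-month ratio runs from 1.00 with complete survey capture, through about 1.00-1.05 at 85%, to about 1.29 at 50% with a 7-day look-back. The corresponding excess is at most about 5 points, or about 10 over weeks 1-12; events clustered during treatment would move the six-month figures towards the 12-week ones. These are scenarios, not bounds.

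The inconsistency between Section 6.2.4 and Sections 7.1 and 7.2 is plain on the text. Whether it affects what participants report is unknown.

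**What to change.** 1. Reconcile Section 6.2.4 with Sections 7.1 and 7.2, so that participants report any new or worsened problem and relatedness stays with the PI or designee. Change the survey item only if its actual wording is narrower.
2. Keep the source or sources of each event (survey, visit, direct report) linked to its AE ID, drawing on the existing visit forms and survey instruments where they already hold it.
3. In Sections 7.1 and 9.5, present non-serious AE rates by arm descriptively with 95% CIs, all-source and survey-reported side by side, with visits per participant. Note that all-source rates may reflect unequal questioning, and that survey-reported rates may miss short-lived events.
4. Keep all sources for SAEs and for follow-up of individuals.

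The cost is a few sentences, at most a source field if the forms lack one, and IRB approval if a participant-facing item changes (Section 11.1). The downsides are two AE tables that may differ, neither free of bias, and possibly a few more unrelated events to adjudicate.
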